We hypothesize that the addition of the Osto-Ring™ will reduce leakage from the stoma appliance and may also increase the length of time needed between pouch changes. Currently, the mean ostomy pouch wear time in the United States is 5.2 days (Richbourg L, Fellows J, Arroyave WD. Ostomy pouch wear time in the United States. *J Wound Ostomy Continence Nurs.* 2008 Sep-Oct;35(5):504-8), and out-of-pocket costs can be as high as \$30 with each pouching system change which translates to a yearly cost of close to \$3000. Longer wear time would therefore translate into needing fewer ostomy bags and less money spent on ostomy supplies.

Overall Objective:

The primary objective of this pre-market study is to assess the safety and performance of the Osto Ring™ as it relates to the pouching system wear time and degree of leakage.

Protocol Version #1
Dated 4/22/19

Research Design:

Study population: 30 adult subjects who have had an ileostomy or colostomy for at least 6 months, who currently use the Hollister New Image 2 piece pouching system acting as their own controls, will use their standard 2 piece New Image Hollister pouching system without the Osto Ring™ for 28 days. On Day 29 subjects will be switched to the Osto-Ring regimen until day 56. Patients will be evaluated in person at Day 0 and approximately Days 28, 56, and 75 (within business days and scheduling convenience).

The Osto-Ring for this study is being supplied by GoDuRn, LCC, and provided to subjects free of charge.

During the standard of care visit to the health care provider, subjects will be evaluated to confirm that they meet the criteria for participating in this study.

Study Design:

Day 0-27

Visit One

- **Subject will wear their standard of care Hollister 2 piece New Image pouching system for 28 days.**
 - At the first visit they will remove their pouching system to allow the investigator to assess their skin (research staff will take photo) using the Ostomy Skin Tool Reference Guide [See appendix B]
 - They will be given and asked to fill out the Quality of Life Questionnaire [See appendix C]
 - They will be given Ostomy Evaluation Record [See appendix A] and asked to complete this at every pouching system change. (And take photos of the skin site and adhesive side of the ostomy flange.)

Day 28-55

Visit Two

- **Subjects will now wear their standard of care Hollister 2 piece New Image pouching system with the Osto-Ring for the next 28 days.**

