To calculate the study sample size, data from prior studies and expert opinion was used for power analysis since this device uses a novel approach to increase wear time. The mean wear time for ileostomy pouches in the United States is 5.01 +/- 2.25 days (Richbourg L, Fellows J, Arroyave WD. Ostomy pouch wear time in the United States. *J Wound Ostomy Continence Nurs.* 2008 Sep-Oct;35(5):504-8). An increase of wear time by 25% to 6.26 days is beneficial for patient care. We determined the effect size to be 0.56 assuming that the pool standard deviation is similar to the study cited above. Using a paired t-test with a significance level of 0.05 and power of 0.8, 27 patients are needed for this study.

All patients will be recruited from the NorthShore University HealthSystem IBD center and General Surgery Clinics. Evaluation and management for any stoma related questions, concerns or assessments may also be provided by our IBD center team. Results of the study will not be made available to the sponsor or anyone with a perceived or actual conflict of interest (eg actual/potential financial relationship) until the statistical analysis has been independently completed.

Inclusion Criteria:

Subjects interested in participating in the clinical investigation must comply with the following criteria:

1. Are at least 18 years of age and have full legal capacity
2. Have had an end or loop ileostomy or colostomy for at least 6 months.
3. Have used a Hollister 2 piece New Image pouching system for at least 8 weeks
4. Able to provide informed consent
5. Have a stoma with a diameter of 57mm or less

Protocol Version #1

Dated 4/22/19

6. Change their pouching system at least two times in seven days

Exclusion Criteria:

Subjects complying with the following criteria must be excluded from participation in the clinical investigation:

1. Unable to give informed consent.
2. Are pregnant or currently breastfeeding.
3. In the last 2 months has received or is currently receiving, chemotherapy or radiation therapy.
4. In the last month has received or is currently receiving systemic or local steroid treatment in the peristomal area.
5. Currently suffering from severe peristomal skin problems such as peristomal pyoderma, abscess.
6. Currently suffering from a peristomal hernia.
7. Known hypersensitivity toward any of the test product (Osto Ring™ is made of surgical grade stainless steel)
8. In the last 30 days has participated or is currently participating in a clinical study

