9. Assessed with an ostomy skin tool score of ≥ 3

Primary Outcomes:

Performance Efficacy:

To evaluate the Osto Ring™ for pouching system wear time, and degree of leakage in subjects when using the Osto Ring™ as compared to when not using the Osto-Ring™

- Integrity of the adhesive side of the flange (photos)
- Wear Time:
 - Total time pouching system worn will be calculated by the Ostomy Evaluation Record. This is defined as the difference between the dates and times the appliance is changed. (Appendix A)
- Leakage:
 - Degree of leakage at time of pouching system changes will be measured using line item from Ostomy Evaluation Record (Appendix A)

Secondary Outcomes:

1. The condition of the peristomal skin and stoma (Appendix B)
2. The number and frequency of adverse events
3. The subjects' quality of life using the Stoma Quality of Life (QoL) questionnaire (Appendix C)
4. Subject Ease of Use (ease of application, pain level with application, comfort, convenience of use) will be assessed using Likert scale: 1 = poor, 2 = satisfactory 3= very good, 4= excellent (Appendix D)

Analysis plan:

Protocol Version #1

Dated 4/22/19

All means and frequencies will be compared between the groups with the Osto Ring™ versus the group without it and will be controlled for the order in which a subject used the Osto Ring.

- Wear Time:
 - Mean days in between pouching system changes
- Leakage:
 - Frequency of any degree of leakage at pouching system changes
 - Frequency of much leakage at time of pouching system change
- Skin condition:
 - % of patients with moderate to severe skin conditions at time of each WOC nurse or physician study visit
 - Mean % of time with moderate to severe skin conditions throughout the 4 week interval at every WOC nurse or physician study visit
- Quality of Life:
 - Mean quality of life scores
- Time per Ostomy Care Session
 - Mean minutes spent during ostomy care session
- Ease of Use
- Mean % of time ease of use reported as very good or excellent by subject , Satisfaction and Confidence
 - Mean satisfaction and confidence scores
- Device Recommendation
 - % of subjects reporting they strongly agree to recommend the device to others

We will compare the baseline characteristics of the two groups. Continuous variables will be compared with the paired *t* test, and categorical variables were compared with the Fisher exact test. Each item on the ostomy evaluation record form will be individually reported.

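### Wear time and two nested forms of leakage are analysed as primary with no order, adjustment or success rule; if any one counts, the chance of a false-positive primary result is up to about 14%

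*Combined protocol and SAP*

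**What the plan says.** The plan gives four signals about what the trial is meant to show, and they do not agree.

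- **Hypothesis** (end of Background and Significance): the ring "will reduce leakage from the stoma appliance and may also increase the length of time needed between pouch changes". Leakage comes first and wear time second.
- **Sample size** (the paragraph before Inclusion Criteria): "Using a paired t-test with a significance level of 0.05 and power of 0.8, 27 patients are needed for this study". The effect size behind it, 0.56, concerns wear time only. This is the only place where a significance level appears.
- **Primary Outcomes, Performance Efficacy**: three items are listed, namely flange integrity from photographs, wear time, and degree of leakage taken from one item of the Ostomy Evaluation Record.
- **Analysis plan**: every mean and frequency is to be compared with and without the ring. Wear time appears as mean days between changes. Leakage appears twice, as "Frequency of any degree of leakage at pouching system changes" and as "Frequency of much leakage at time of pouching system change". Flange integrity does not appear.

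The Analysis plan names a paired t test for continuous variables and the Fisher exact test for categorical ones. It gives no significance level, order of testing, adjustment for several primary measures, or rule for declaring success.

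**The concern.** With several primary measures and no decision rule, nothing fixes in advance which result decides the trial. The sample size points to wear time, the hypothesis points to leakage, and the outcome list treats them as equals. A single nominally significant result on any of them could be reported as a primary outcome met, whatever the others show. The 0.05 used to size the trial would not describe the error rate of that claim.

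This matters for a pre-market study of performance. The protocol already withholds results from the sponsor and conflicted parties until an independent analysis is complete. An open choice among primary results weakens that protection.

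**Working it through.** **Step 1: reproduce the plan's own figure.** From the sample-size paragraph: reference mean 5.01 days, SD 2.25, target 6.26 days, level 0.05, power 0.8.

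- Effect size: (6.26 − 5.01) / 2.25 = 1.25 / 2.25 = 0.556, stated as 0.56.
- Paired t test power from the noncentral t distribution, with n − 1 degrees of freedom and noncentrality 0.56 × √n. At n = 27 and two-sided 0.05, power is 0.7998.
- A one-sided 0.05 test would need only 20-22 patients, so 27 is a two-sided figure. The plan's number reproduces.

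**Step 2: count the primary comparisons that have a planned analysis.** There are three: mean wear time, any leakage and much leakage. Flange integrity has no scale, summary measure or test, so it is not counted.

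**Step 3: error rate if any one significant result counts.** Assume each comparison is tested at two-sided 0.05. With m independent tests the chance of at least one false positive in either direction is 1 − 0.95^m. The chance of at least one in the device's favour is 1 − 0.975^m.

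| Tests | Either direction | Device's favour |
|---|---|---|
| 1 | 5.0% | 2.5% |
| 2 (wear time, one form of leakage) | 9.75% | 4.9% |
| 3 (the analysed comparisons) | 14.3% | 7.3% |
| 4 (only if flange integrity were tested) | 18.5% | 9.6% |

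**Step 4: allow for correlation.** Any and much leakage are nested cut-points of one item, so they are positively correlated. The plan gives no correlations, so the values below are assumptions. They come from 200,000 simulated trials of three paired t tests with n = 27 and a common correlation.

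| Correlation | Either direction | Device's favour |
|---|---|---|
| 0.3 | 13.7% | 6.9% |
| 0.5 | 12.7% | 6.4% |
| 0.7 | 11.2% | 5.6% |
| 0.8 | 10.0% | 5.0% |

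A less uniform pattern gives similar results. With 0.7 between the two leakage measures and 0.3 between each of them and wear time, the figures are 12.6% and 6.3%.

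**Step 5: wear-time power under two remedies**, at the plan's effect size of 0.56.

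| Completers | Wear time tested first at 0.05 | Bonferroni over three tests, 0.05 / 3 = 0.0167 |
|---|---|---|
| 27 | 0.80 | 0.64 |
| 30 | 0.84 | 0.70 |

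Bonferroni over three tests would need 37 patients to restore 80% power.

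**The case against.** The strongest reply is that the plan never says one significant result is enough. If both wear time and leakage had to succeed, there would be no inflation. That stands: the error rate depends on a success rule that the plan does not state. The fault is the silence, because the text permits either reading after the data are seen.

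A reader might go further and infer that four measures are each tested at 0.05, so that a false claim for the device has a probability of 13-19% instead of 5%. The documents do not support that, for four reasons.

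- **The fourth test is not planned.** Flange integrity is listed as primary but is absent from the Analysis plan. Both ends of 13-19% need it: 18.5% is four independent tests, and about 13% is four tests correlated at 0.7.
- **The direction is wrong.** Those figures count false positives both for and against the device. In its favour the rate is about half as large, and the single-test comparator is 2.5%, not 5%.
- **The level is inferred.** The plan states 0.05 for wear time only. No other level appears, so 0.05 is the natural assumption for leakage, but it remains an assumption.
- **Independence is a ceiling.** The two leakage measures come from one question. Counted as one outcome, leakage and wear time give at most 9.75% in either direction and 4.9% in the device's favour.

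Two further effects cannot be sized from the documents. The discreteness of the Fisher test may lower the leakage error rates. Treating repeated changes in one subject as independent could raise them.

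**Conclusion.** The concern holds in a limited form. The plan has more than one primary outcome, analyses leakage in two nested ways, and fixes neither a deciding endpoint nor a success rule.

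If any one of the three analysed comparisons counts as success at two-sided 0.05, the chance of at least one false-positive primary result is at most 14.3%, and about 10-14% at correlations of 0.3-0.8. In the device's favour it is at most 7.3%, against 2.5% for a single test.

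These figures rest on three assumptions: the any-one success rule, the use of 0.05 for leakage, and the correlations. The ceilings also take each test to hold its nominal level and the measures not to be negatively correlated in the direction of benefit. Without that last condition the simple sums, 3 × 0.05 = 15% and 3 × 0.025 = 7.5%, are the bounds, which changes little. The point should be corrected before analysis. It does not call the design or the sample size into question.

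**What to change.** Add to the Analysis plan:

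1. Mean wear time, the endpoint on which the sample size is built, is the single primary endpoint, tested at two-sided 0.05.
2. Any leakage is tested next at two-sided 0.05, only if wear time is significant. Much leakage follows at two-sided 0.05, only if any leakage is significant.
3. Flange photographs are reported descriptively and support no significance claim.

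Bring Primary Outcomes into line with this. The fixed order holds the familywise error at 5% whatever the correlations, provided each test holds its level. It leaves wear-time power as planned: about 0.80 with 27 completers, and 0.84 only if all 30 complete.

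The change takes a few sentences and needs no extra patients or data. The real cost falls on leakage, which the hypothesis puts first: it loses its primary status and can be claimed only if wear time succeeds. The sample size argues for wear time first and the hypothesis argues the other way, so the sponsor should confirm the order before any data are analysed. Requiring both wear time and leakage to succeed would also close the gap, but the plan gives no leakage inputs from which to work out the power of that rule.

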Safety Assessments and Termination Guidelines

WOC nurses will perform skin assessments at key times. Patients are to be told that they must mention any deviation from their baseline ostomy pouching system changing routine. Failure to do so will result in a protocol violation. Patients receiving an Ostomy Skin Tool score of ≥ 3 without a known cause will be withdrawn from the study.

Any patient suffering an allergic reaction to either product (the standards New Image Hollister appliance or Osto Ring) or suspected of having an adverse reaction of any kind as determined by the patient and/or the ostomy will be removed from the trial, return for clinical assessment as indicated and return to their standard stoma care appliance.

The data safety monitoring committee will consist of Drs [name] and [name], who will review any unanticipated adverse events and have the authority to stop the trial at any time if any safety concerns are raised.

Osto-Ring™ Risks

Side effects may include:

- allergic reaction to the ring,
- worsening of the peristomal skin condition, or
- prolonged time needed in changing the ostomy pouching device.

2-piece New Image Hollister Pouching System

The 2 piece New Image Hollister Pouching System is standard of care. Concerns regarding this system will be handled by the regular physician. However, all concerns will be addressed.

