Appendix A

OSTOMY EVALUATION RECORD

ID Number: _____ Date: _____

Number of days since last Change: _____

Please respond to each of the following items describing your experience in between pouching system changes. One Ostomy Evaluation Record should accompany EACH Ostomy Change

1. What was your average wear time (time between placing the pouching system on and taking it off) _(days)_____

2. Did you notice any skin damage around your stoma, redness and open areas? Yes or No

3. Did you note any odor from the ostomy between appliance changes?

No odor

Slight odor

(Skip to Question 3)

Strong odor

4. How bothersome did you consider the odor?

Not at all bothersome

Protocol Version #1

Dated 4/22/19

- Slightly bothersome
- Moderately bothersome
- Severely bothersome
- Extremely bothersome

5. Did you encounter leakage and if so how much?

- | | |
|-------------------------------------|---|
|  No leakage |  Slight leakage |
| (Skip to Question 7) |  Much leakage |

How many days was the pouching system in place before you noted leakage? _____

6. How bothersome did you consider the leakage?

- | | |
|--|---|
|  Not at all bothersome |  Severely bothersome |
|  Slightly bothersome |  Extremely bothersome |
|  Moderately bothersome | |

7. Was your social freedom limited by your ostomy?

- | | | |
|---|---|--|
|  Not limited at all |  Slightly limited |  Greatly limited |
| Somewhat unaccepting | | |
|  Very unaccepting | | |

8. How convenient was your ostomy care?

- Very convenient
- Somewhat convenient
- Neutral
- Somewhat inconvenient
- Very inconvenient

8. How satisfied were you with your ostomy care?

- Very satisfied
- Somewhat satisfied
- Neutral
- Somewhat dissatisfied
- Very dissatisfied
- Somewhat dissatisfied
- Very dissatisfied

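### Minutes per ostomy care session are to be compared with and without the ring, but no form or visit procedure shown records them, so a listed ring risk would go unquantified

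*Combined protocol and SAP*

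**What the plan says.** The Analysis plan has an entry for time per care session, specified as "Mean minutes spent during ostomy care session". It falls under the general rule that opens the section: "All means and frequencies will be compared between the groups with the Osto Ring™ versus the group without it". The measure is therefore needed in both 28-day periods.

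The Osto-Ring Risks list, under Safety Assessments and Termination Guidelines, gives three possible side effects. One is "prolonged time needed in changing the ostomy pouching device".

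Data at each change come from Appendix A in both periods ("One Ostomy Evaluation Record should accompany EACH Ostomy Change") and, in the ring period only, from Appendix D as well. Session time is in neither the primary nor the secondary outcome list. It appears only as a line in the Analysis plan.

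**The concern.** A planned mean needs a recorded variable. The outcome lists tie wear time, leakage, skin condition, quality of life and ease of use each to an appendix. Session time is tied to none, and no item on the forms shown would supply it.

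The stakes are moderate. The overall objective covers safety as well as performance, and minutes per change is the only planned analysis that would put a number on the longer-change risk. Without it, the trial could report a gain in wear time but not what that gain costs the subject in minutes at each change.

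The gap is also hard to repair afterwards. All subjects wear the standard system first and move to the ring at about Day 28. Once a subject's first period has ended, minutes per change without the ring could be obtained only from memory.

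**Working it through.** The plan gives no figure for session time, so there is none to reproduce. Its one computed figure is the sample size for wear time. The effect size is (6.26 − 5.01)/2.25 = 0.556, given as 0.56. A two-sided paired t test at 0.05 with that effect has power 0.7998 at n = 27, which rounds to the stated 0.80. Nothing below depends on this figure.

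**Step 1: look for a source of session minutes.**

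| Source | When used | Time information | Gives session minutes? |
|---|---|---|---|
| Appendix A, header | Each change, both periods | Date; "Number of days since last Change" | No: interval in days |
| Appendix A, item 1 | Same | Wear time in days | No: time the system was on |
| Appendix A, follow-up to item 5 | Same | "How many days was the pouching system in place before you noted leakage" | No: days to leakage |
| Appendix A, first item 8 | Same | "How convenient was your ostomy care" | No: ordered categories |
| Appendix B | Visits | None (skin score) | No |
| Appendix C | Visits One to Three | None in the items shown | No |
| Appendix D | Each change, ring period only | None (ratings and free text) | No, and no data without the ring |
| Visit procedures, Study Design | Visits | No timing of a change described | No |

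The wear-time definition under Primary Outcomes uses the dates and times of changes. One time stamp per change gives the interval between changes. The length of a change needs a start and a stop, or a stated duration.

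**Step 2: what one added line would yield.**

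Inputs:
- 30 subjects (Research Design)
- 28 days, or 4 weeks, per period (Study Design)
- at least two changes in seven days at entry (inclusion criterion 6)
- a 25% increase in wear time (sample size paragraph)

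Without the ring, at the entry minimum: 30 × 2 × 4 = 240 records. This is a floor, because the criterion is itself a minimum.

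With the ring, the entry rate cannot simply be carried over, since the device is meant to reduce the number of changes. Two changes a week is one every 7/2 = 3.5 days. With 25% longer wear, 3.5 × 1.25 = 4.375 days. Changes per subject are 28/4.375 = 6.4, and 30 × 6.4 = 192 records.

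Total: 240 + 192 = 432. Both counts assume that every subject finishes and every form is completed. They show yield only. A paired comparison of subject means rests on about 30 pairs, however many sessions are recorded.

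**The case against.** **The form shown may not be complete.** Appendix A has two acceptance options stranded under item 7, which asks about social freedom. It also has two items numbered 8 and a repeated pair of dissatisfaction options at the end. Item 1 of Appendix D has a scale but no question, and Appendix C passes from item 8 to item 16. A reader might take the run of numbers in Appendix A as proof that nothing was lost. It is not: an acceptance item may have dropped out without leaving a gap. Whether this is damage in reading the PDF or loose drafting cannot be settled from the text. This objection stands as a limit on certainty. It does not supply the missing item: the stray options belong to acceptance and satisfaction scales, and Appendix C is not completed at each change.

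**The risk is not left unmeasured.** A reader might infer that longer change time would go entirely unobserved. The documents do not support that. Subjects must mention departures from their usual changing routine and are asked about side effects at Visit Three, and adverse events are a secondary outcome. Appendix A rates convenience in both periods, and Appendix D covers ease and problems with the ring. None of these yields minutes, and the Appendix D items have no counterpart without the ring. The accurate statement is that the risk is not quantified in minutes.

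**The measure is minor.** This is fair. It is not a listed outcome, and deleting the line would also make the plan consistent.

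**Conclusion.** The mismatch between the Analysis plan and the forms as shown is real and should be resolved. From the data collection the documents describe, the comparison of session minutes cannot be produced, and one of three named ring risks would be captured only indirectly. That no source exists anywhere would be too strong a conclusion, since a fuller copy of Appendix A might carry the item.

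A reader might also suppose that at least 240 records would be available in each period. That floor holds only without the ring. Under the plan's own target the ring-period figure at the entry minimum is about 192, and withdrawals would lower both.

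The conclusion rests on the appendices as they appear here and on there being no unlisted data source. Wear time, leakage and the sample size are unaffected.

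**What to change.** Before the first subject starts, check the source copy of Appendix A. If it already asks for session minutes, no change is needed.

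If it does not, take one of two courses:

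- Add one line to Appendix A, in both periods, asking for the minutes taken for that change. Average within subject and period, and compare the subject means with the paired t test that the Analysis plan already names for continuous variables. The cost is one line on a form already completed at every change.
- If the measure is not wanted, delete the entry from the Analysis plan. This costs nothing, but the longer-change risk then rests on the indirect reports alone, and the protocol should say so.

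### Leakage, a primary outcome, has no stated unit of analysis and no within-subject test, and the only categorical test named ignores pairing

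*Combined protocol and SAP*

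**What the plan says.** Research Design has 30 subjects "acting as their own controls". All of them wear the standard system for 28 days first, and then: "On Day 29 subjects will be switched to the Osto-Ring regimen until day 56". Primary Outcomes states: "Degree of leakage at time of pouching system changes will be measured using line item from Ostomy Evaluation Record". Appendix A is filled in once per change and grades leakage as none, slight or much.

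The Analysis plan lists two leakage summaries: "Frequency of any degree of leakage at pouching system changes", and the corresponding frequency for much leakage. Its opening sentence compares means and frequencies with and without the ring and promises that they "will be controlled for the order in which a subject used the Osto Ring". It names no test and no model.

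Tests appear only in the closing paragraph of that section. It begins "We will compare the baseline characteristics of the two groups". The next sentence gives continuous variables the paired t test and says that "categorical variables were compared with the Fisher exact test". No other test is named for any outcome. Skin condition has two summaries: the percentage "of patients with moderate to severe skin conditions at time of each WOC nurse or physician study visit", and a mean percentage of time.

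**The concern.** Fisher's exact test compares proportions from two separate sets of independent observations. Leakage records are neither separate nor independent: each subject contributes to both periods (pairing) and several times within each period (clustering).

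The recording unit, one pouch change, is clear. The unit of analysis is not. A frequency at changes could be a proportion of all changes pooled over subjects, or an average of per-subject shares, and these call for different tests.

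Reducing leakage is the first hypothesis stated in the Background. As written, either an unsuitable test is applied to a primary outcome, or its unit and test stay open and could be settled after the data have been seen.

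**Working it through.** **1. The plan's own figure.** There is none for leakage. The only sample size, 27, is for wear time: (6.26 - 5.01)/2.25 = 0.556, taken as 0.56. A two-sided paired t test with n = 27 then has power 0.7998, so the figure reproduces. It gives no information about leakage.

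**2. Records per subject.** Inclusion criterion 6 requires at least two changes in seven days. If that habit continues, 2 x 28/7 = 8 records per subject per period, or 30 x 8 = 240 per period. There may be fewer with the ring if wear lengthens.

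**3. Two readings of the test sentence.**
- *It covers outcomes.* The word paired supports this, since a paired test has no use in comparing the baselines of two groups. Fisher is then the rule for categorical outcomes, which are paired here. The paired t test would fit leakage only if frequency meant a per-subject share, which the plan does not say.
- *It covers baseline only.* The preceding sentence supports this. Leakage then has no named test. The baseline comparison has no object either, because one group of subjects supplies both periods.

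**4. Why the direction is open if changes are pooled.** Let a subject's leak probability p vary, with σ² the part of its variance shared by both periods and τ² the part specific to a period. With N subjects and m changes per period:
- true variance of the difference in pooled proportions = (2/Nm) x [E{p(1-p)} + mτ²]
- variance under Fisher's independence assumption = (2/Nm) x [E{p(1-p)} + σ² + τ²]

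Fisher understates the variance when (m - 1)τ² > σ² and overstates it when the inequality is reversed. At m = 8 the boundary is τ² = σ²/7. The documents give neither quantity.

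**5. Size under assumed inputs.** All inputs except N are assumptions: N = 30; 8 v 8 or 8 v 6 changes; median leak probability 0.2 or 0.4; stable subject SD 1 or 2 on the logit scale; subject-by-period SD as shown. There were 10,000 simulated trials per setting, with no true difference and a nominal level of 5%.

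| Subject-by-period SD | Fisher, pooled changes: type I error |
|---|---|
| 0 | 0.9-2.9% |
| 0.5 | 2.5-5.5% |
| 1.0 | 7.5-13.6% |
| 1.5 (extreme) | 13.9-21.4% |

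A paired t test on per-subject shares stays at 4.6-5.6% throughout.

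**6. Power, at an assumed log-odds effect of -0.6.** At SD 0 the paired test has 52-79% and Fisher 35-74%, a difference of 5-21 points. At SD 0.5 the picture is mixed: with subject SD 1, Fisher has about 3-4 points more; with subject SD 2, the paired test has 7-10 points more. At SD 1.0 and above Fisher does not hold its level, so its rejection rate cannot be read as power.

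**7. Per-subject yes/no outcomes.** The skin percentage is of this kind. Fisher uses only the two margins, whereas McNemar uses the subjects who change. As arithmetic only, 12/30 v 5/30 gives Fisher p = 0.084 whatever the pairing. Exact McNemar on the same margins runs from 0.016 (7 improve, 0 worsen) to 0.143 (12 improve, 5 worsen). These margins are invented. They match no stated leakage summary, and they are not a forecast for skin, where Exclusion criterion 9 removes scores of 3 or more at entry. The mean percentage of time with skin problems is a per-subject quantity and can use the paired t test.

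**8. Order.** Every subject uses the ring second. An order variable is constant across subjects, and a period variable coincides with ring use. Neither can be adjusted for, so the promise in the opening sentence does not fill the gap.

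**The case against.** The strongest reply is that a valid test is already in the plan. The paired t test is named in the Analysis plan and used for the sample size, subjects are their own controls, and a per-subject percentage already appears for skin. What is missing is then one definition. This largely stands, and it is why the remedy is small. It does not dispose of the point, because the plan gives the paired t test to continuous variables and never turns the graded leakage item into one.

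Several stronger readings are tempting, and the documents do not support them:
- *That the plan prescribes Fisher for leakage.* This is an inference. The clause follows a baseline sentence and is in the past tense, so it may be template wording.
- *That false positives will be inflated.* Error above about 5.5% needs three things together: Fisher covers outcomes, changes are pooled, and subject-by-period SD is about 1.0 or more. None is established. At SD 0 to 0.5 Fisher is conservative or near nominal.
- *That a paired test brings a general gain in power.* The 5-21 points hold only at SD 0.
- *That the test will be picked after seeing the data.* It could be; nothing says it will. The protocol withholds results from the sponsor and conflicted persons until independent analysis is complete. That is a partial safeguard: it limits who sees results, not when the test is fixed.

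The fixed order is a separate and larger weakness of the design. No choice of leakage test repairs it, and it does not add to the weight of this point.

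**Conclusion.** The point holds on the text and should be fixed, though it falls short of a must-fix. For a primary outcome recorded repeatedly by the same subjects, the plan defines no unit of analysis and assigns no within-subject test. If the one categorical test it names were applied to leakage or to the skin percentage, its p-value would be invalid. If that test is for baseline only, leakage has no test and the baseline comparison is void.

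Neither the size nor the direction of harm can be shown from the documents, which give no leak rate and no within-subject correlation. The simulated range, from about 1% to 7.5-13.6% at a subject-by-period SD of 1.0 and up to 21.4% in an extreme setting, shows only that pooled Fisher cannot be relied on to hold 5%. It rests on assumed inputs and on pooling, which the plan does not state.

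**What to change.** In the Analysis plan:
- For each subject and period, define the share of changes with any leakage and the share with much leakage. Compare each within subject by the paired t test, with the Wilcoxon signed-rank test as a sensitivity analysis.
- Replace Fisher by exact McNemar for per-subject yes/no outcomes, such as the percentage of patients with moderate to severe skin conditions.
- Describe baseline once, without a test.
- Delete the order adjustment, and state that order is fixed and cannot be separated from the ring.
- Optionally, also report leaking changes per 28 wear-days, because the share of leaking changes can rise merely because each wear lasts longer.

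The cost is a few sentences and a little analysis work, best settled before any outcome data are examined. No new data are needed: Appendix A already records the degree of leakage and the days since the last change.
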